Participating orthopaedic surgeons and the study coordinator will be responsible for case finding and subject recruitment. Patients will be screened and those found eligible will be offered participation. Informed consent will be obtained from the patient or from a parent or legal guardian for patients less than 18 years of age.

D.1.a. Inclusion criteria: Patients must meet all of the following criteria to be *eligible*: (1) Age 3 to 18 years on day of surgery, (2) diagnosis of spinal deformity, (3) undergoing elective posterior spine multi-level instrumentation surgery

D.1.b. Exclusion criteria: Patients having any of these criteria will be *ineligible*: (1) Documented renal failure, (2) documented allergy to iodine or shellfish, (3) previous spine fusion surgery, (4) undergoing elective posterior spine instrumentation surgery fusing fewer than six levels, (5) undergoing anterior or anterior-posterior spine multi-level instrumentation surgery; (6) current antibiotic use.

D.2. Randomization and Blinding

Patients will be randomized to saline or povidone-iodine & saline irrigation via an envelope system. Patients will be blinded to the type of irrigant used. Ideally, surgeons would also be blinded to treatment group; however, it is not possible because they will be irrigating the surgical wound in the operating room and the two solutions will be identifiable because they are a different color.

D.3. Description of Study Treatments

D.3.a. Standardization of Periprocedure interventions

All patients will receive cefazolin (25 to 50 mg/kg, dependent on standard of care) IV within one hour prior to skin incision. Patients will also receive IV gentamycin or tobramycin (2.5 mg/kg) every 8 hours if they have a neuromuscular diagnosis. Appropriate every 3 or 4 hour (according to standard of care) dosing will be continued intraoperatively and for 24 hours post-operatively. If a patient allergy to cefazolin exists, clindamycin dosed every 6 hours or vancomycin dosed every 12 hours may be substituted. Skin will be prepped with chlorhexidine.[24] Surgical approaches, fusion levels, deformity correction techniques, and hardware selection will be at the discretion of the surgeon.

D.3.b. Standardization of Culture/Irrigation Procedure

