Prior to closure, a swab or tissue of the surgical wound will be performed (aerobic cultures) to establish the baseline incidence of bacterial contamination. This will be performed by excising the tissue or swabbing the wound under the retractor at the inferior aspect of the wound, using the routine surgical pathology protocol of the institution. Following, any nonviable tissues will be debrided and the irrigant solution (0.35% povidone-iodine or sterile saline) of sufficient volume to fill the wound will be in contact with all areas of the wound for three minutes. A second sample (aerobic cultures) will be collected immediately after lavage with saline or povidone-iodine from the same location to determine reduction in the incidence of bacterial contamination achieved by

each irrigant. This sample will be obtained prior to placement of bone graft/antibiotics to obtain samples as close to closure as possible without allowing the application of local antibiotics to influence the results. A further 2 liters of normal saline will then be used for the povidone-iodine treatment group to irrigate the wound further which will remove traces of the iodine irrigant from the surgical site. If deemed appropriate by surgeon, a patient in the saline treatment group will then be irrigated with povidone-iodine and saline as per standard of care. Use of pulse or low pressure lavage will be up to the discretion of the surgeon.

D.4. Definition of Endpoints

(1) Proportion of patients with an initial positive bacterial culture prior to irrigation (2) Bacteriology of tissue in cases of positive cultures, and (4) Proportion of patients with a positive bacterial culture after irrigation

D.5. Data Collection Methods, Assessments and Schedule

Data will be collected on standardized paper case report forms (CRF) by the study coordinator and entered into a study-specific REDCap database. Study data will be collected at the pre-operative consultation, and during surgery (see Table 1.) Wound cultures will be tested specifically for research to evaluate the efficacy, respectively, of *povidone-iodine*.

Table 1. Schedule of Measurements

Measurement	Baseline (Pre-Operative)	Surgery
Demographics	X	
Medications	X	
Medical history	X	
Laboratory results	X	X
Surgical site cultures (2)		X
Surgery/OR data		X

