Demographics, medications, medical history, and laboratory results will be collected from medical records. Surgical data will be collected during the fusion operation and two standard cultures of the surgical site will be taken during the surgery using the routine surgical pathology protocol at each institution. Results from the cultures taken at the fusion operation, in addition to any other associated post-operative cultures, will also be collected post-operatively from medical records.

D.6. Adverse Events and Reporting Procedures

The only foreseeable, but highly unlikely adverse event associated with participation in this trial is an increased level of iodine in the blood as a result of washing the wound site with povidone-iodine. Extra iodine in the body is excreted through urine. A healthy body without thyroid or renal abnormalities is able to excrete excess iodine without any problems.

The monitoring of adverse events will be conducted on an ongoing basis for the duration of the study. If an adverse event occurs, it will be reported immediately to the IRB and the investigators will re-assess the risk/benefit ratio of the study and submit any modifications deemed necessary to the IRB for approval.

D.7. Statistical Considerations

We project an accrual of 150 patients, resulting in 75 per treatment group. Patients will be recruited from “low risk” and “high risk” patient populations in a 3:1 fashion, respectively. “Low risk” patients are defined as those with an idiopathic condition and the “high risk” group will encompass all others. Within each patient “risk” group, randomization will be split evenly between saline and betadine in a 1:1 fashion. Positive cultures before and after irrigation will be monitored to establish the efficacy of povidone-iodine irrigation. 150 patients will provide good statistical precision for estimating the probability of a positive pre-irrigation culture, as shown in the following table. The table shows exact 95% confidence intervals (CI) for the estimated percentage over a plausible range of observed outcomes.

Observed percentage:	30/150=20%	37/150=24.7%	45/150=30%
95% CI:	(14%, 27%)	(18%, 32%)	(23%, 38%)

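### The post-irrigation culture is taken while iodine is still expected in the povidone-iodine wound and no neutralising step is stated, so any suppressed growth would bias endpoint (4) towards povidone-iodine

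*Combined protocol and SAP*

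**What the plan says.** Section D.3.b sets this order: a baseline sample; debridement; the irrigant (0.35% povidone-iodine or sterile saline) held in the wound for three minutes; and then the second sample. On the last step it says: "A second sample (aerobic cultures) will be collected immediately after lavage with saline or povidone-iodine from the same location". After that sample, the povidone-iodine group receives 2 litres of saline to "irrigate the wound further which will remove traces of the iodine irrigant from the surgical site".

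The second sample is placed before bone graft and antibiotics, "without allowing the application of local antibiotics to influence the results". No comparable precaution is stated for the irrigant.

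The specimen may be obtained by "excising the tissue or swabbing the wound under the retractor at the inferior aspect of the wound". Handling is left to the sites. D.5 says that "two standard cultures of the surgical site will be taken during the surgery using the routine surgical pathology protocol at each institution". No neutralising medium, inactivation step or carry-over check is described.

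The second sample supplies endpoint (4) in D.4: "Proportion of patients with a positive bacterial culture after irrigation".

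**The concern.** Two different things can make the second culture negative. Bacteria may have been killed or washed away in the wound, which is the treatment effect. Or bacteria that were viable at sampling may fail to grow because iodine came along in the swab or tissue, which is measurement error. The planned data cannot separate the two.

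Randomisation does not help, because carry-over follows the assigned arm. The other antibacterial exposures described before the second sample do not differ by arm: D.3.a provides prophylactic antibiotics irrespective of arm, and "Skin will be prepped with chlorhexidine". In the stated procedures the study irrigant is therefore the only iodine source before that sample and the only antibacterial agent that differs between arms.

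At stake are endpoint (4), the effect estimate in aim 5 (section A) and the post-irrigation part of the interim comparison (section G). Section B makes a larger trial conditional on a reduction in contamination and gives no numeric threshold, so a distorted estimate could also mislead the planning of that trial. The pre-irrigation endpoints are unaffected.

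**Working it through.** **Which steps can bias the sample.** The 2-litre rinse comes after the second sample, so it is not itself a source of bias. The same holds for the option in D.3.b that reads "If deemed appropriate by surgeon, a patient in the saline treatment group will then be irrigated with povidone-iodine and saline": it too follows the sample. What remains is iodine present at the moment of sampling, in one arm.

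**Inputs from D.7 and G.** 75 patients per arm; post-irrigation positive rate .12 with saline and .05 projected with povidone-iodine; two-sided chi-square test; final criterion p<.0451; interim criteria p<.001 and p<.0141 at about 1/3 and 2/3 of accrual, taken here as 25 and 50 per arm.

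**Input not in the documents.** f is the share of contaminated povidone-iodine specimens in which growth is suppressed. It is assumed, over 0 to 50%, and may differ between swab and tissue.

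**Reproducing the plan.** For .12 vs .05, exact binomial enumeration gives 79.2% for at least 3 fewer positives (D.7: 79%). The pooled normal approximation gives power of 33.5% (D.7: 33%). The plan's arithmetic is not in question.

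**Model.** Observed povidone-iodine rate = true rate × (1 − f), with the saline rate unchanged. Hence apparent RR = true RR × (1 − f).

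**No true effect (.12 in both arms).** The chance of a significant result favouring povidone-iodine comes from exact enumeration of two independent binomials with the uncorrected chi-square:

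| f | Expected povidone-iodine rate | Apparent RR | Favourable result, final analysis only | Favourable result, with both interim looks |
|---|---|---|---|---|
| 0% | .12 × 1.00 = .120 | 1.00 | 2.4% | 2.6% |
| 10% | .12 × .90 = .108 | .90 | 4.0% | 4.3% |
| 25% | .12 × .75 = .090 | .75 | 8.3% | 8.7% |
| 50% | .12 × .50 = .060 | .50 | 23.8% | 24.5% |

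The last column treats the stopping boundaries as strict, for calculation only, since section G calls them a guideline. Using the t-test that section G names at the interim looks leaves the values unchanged to four decimals. In the final-only calculation the favourable chance reaches 5% at f of about 14% and 10% at about 29%.

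**Projected effect true (.12 vs .05).** RR .05/.12 = .417 becomes .417 × .90 = .375, .417 × .75 = .313 and .417 × .50 = .208 at f = 10, 25 and 50%. The favourable chance at p<.0451 goes from 32.3% to 37.3, 45.8 and 62.0%.

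**Reading an observed .05 backwards.** The true rate would be .05/(1 − f): .056, .067 or .100 at f = 10, 25 or 50%, so a true RR of .46, .56 or .83. At f = 1 − .05/.12 = 58%, the whole projected difference would arise with no true benefit.

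**The case against.** The strongest objection is that the causal chain is not in the documents. They support iodine traces in the wound before the rinse. Bias also needs iodine to enter the specimen, stay active in the laboratory and stop viable organisms growing, and no section says that any of this happens. Section C calls the disinfecting ability theoretical and speaks of the wound, not the culture. This stands, and it limits the point to an uncontrolled risk of bias.

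Second, laboratory handling is delegated to site protocols that are not visible here, and some may already neutralise iodine. This also stands. The claim is only that neutralisation is neither stated nor standardised.

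Third, f is assumed, one constant f is a simplification, and the larger probabilities exist only because 50% was included. Significance is also a poor yardstick for a pilot that concedes low power in D.7. This is fair: the probabilities are illustrative, and RR × (1 − f) is the more relevant figure. But D.7 offers preliminary information on effect size as the pilot's value, which is the quantity that carry-over would distort.

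Fourth, the remedy also changes the pre-irrigation specimen, where no bias is identified, and departs from routine culture. That is a real cost. Handling both specimens alike keeps the before and after cultures comparable.

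**Conclusion.** The concern holds as a possible bias in one direction, of unknown size, in endpoint (4). That the sample precedes the rinse, that traces are expected in one arm only, and that no neutralisation is stated all follow from D.3.b and D.5. That growth is actually suppressed is not shown. If f is 10% or less the distortion is small (apparent RR no lower than .90 with no true effect). At 25 to 50% the apparent RR would be .75 to .50 with no true effect. The analysis cannot correct for this, because f would not be observed. It would not by itself establish a clinical benefit, since the later trial would assess infection. This should be fixed; confidence is medium, because the laboratory protocols are unseen and f is unknown.

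**What to change.** Amend D.3.b so that both samples, swab or tissue, in both arms and at all sites, are collected into or processed with a medium containing an iodine neutraliser agreed with each site laboratory. Where a site's routine handling already does this, D.3.b need only say so. The irrigation sequence and the sampling time stay unchanged.

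The cost is a protocol amendment, a change of collection or processing medium, and agreement with each laboratory, including on tissue specimens, since this may depart from routine handling. No extra patient, visit or specimen is needed. The documents give no cost figure, but the change looks cheap. If it is made after accrual has begun, record which handling each specimen received, because earlier and later specimens would otherwise be mixed without distinction.

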It will be of interest to examine how the tissue colonization rate varies across subgroups such as neuromuscular and idiopathic patients, which we anticipate to accrue in approximately a 3:7 ratio. Under this assumption, and assuming an overall pre-irrigation colonization rate of 25% and a two-sided $\alpha=.05$ test there will be 69%, 90% and 98% power, respectively, to detect relative risks (RR) of 2.0, 2.5, and 3.0, respectively.

Finally, we expect that the probability of a positive post-irrigation culture in the control group will be about .12, with a further reduction to perhaps .05 in the povidone-iodine group. These results would correspond to a relative risk (RR) of .417. Because positive post-irrigation cultures are projected to be fairly rare events, the size of this pilot study will not provide high statistical power unless the true treatment effect is quite large. However, the study should provide useful preliminary information about the size of the treatment effect. For example, the following table shows the probability that the estimated positive culture rate in the povidone-iodine group that will be at least 4, 5.33, 6.67 or 8 percentage points lower than in the control group, assuming the true control rate is .12 and the true rate in the povidone-iodine group is .05, .04 or .03 (corresponding to RR's of .417, .33 and

.25, respectively. Calculations are based on exact binomial probabilities. Also shown is the power of the study under each set of assumptions, assuming a two-sided $\alpha=.05$ chi-square test.

Number of fewer pos. cultures (of 75) in treatment group.	Observed percentage point reduction	True rates RR		True rates RR		True rates RR	
		.12 vs .05	.417	.12 vs .04	.33	.12 vs .03	.25
≥ 3	$\geq 4\%$ reduction	79%		86%		91%	
≥ 4	$\geq 5.33\%$ reduction	70%		78%		85%	
≥ 5	$\geq 6.67\%$ reduction	58%		67%		76%	
≥ 6	$\geq 8\%$ reduction	47%		54%		65%	
	Power:	33%		43%		55%	

For example (see bolded entry), if the true rates of post-irrigation positive cultures are .12 and .05 in the control and povidone-iodine groups, respectively, corresponding to $RR=.417$, there is a 79% chance that the observed rates will differ by 4 percentage points or more (i.e., 3 or fewer positive cultures out of 75 in the treatment group compared with the number of positive cultures out of 75 in the control group). However, there is only a 33% chance of finding a statistically significant difference (power=33%).

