The principal investigator will conduct an evaluation of the progress of the research study on a quarterly basis including assessments of data quality and timeliness; participant recruitment, accrual, and retention; and a review of outcome and complication data to determine whether there is any change to the anticipated benefit-to-risk ratio of study participation and whether the study should continue as originally designed, should be changed, or should be terminated. A summary of these reports will be submitted to sites IRBs and to BCH as part of the annual renewal.

G. Data Safety Monitoring Plan

To ensure safety, an independent safety monitor will be appointed to assist with interim data review. The monitor and the study statistician will be completely unblinded to treatment-group-specific results. There will be one scheduled interim analysis, conducted when data from approximately 1/3 and 2/3 of the accrual goal become available. Interim analysis will focus on the comparison of the treatment groups with respect to the primary endpoint, positive culture rate before and after irrigation, using two-sample t-tests. A "stopping rule" using a truncated O'Brien-Fleming procedure will be used to guide the need for further discussion of the possibility of early stopping among a wider group, including the study investigators. (This rule will not be interpreted strictly but rather will be used as a guideline to trigger the need for a wider discussion.) Specifically, the rule is that the stopping boundary is met if the nominal p-value is $p<.001$ at the first look or $p<.0141$ at the 2nd look. The actual O'Brien-Fleming rule would use a nominal p-value boundary of $p<.00052$ at the first look but this is extremely conservative (i.e., it would take an extreme treatment effect to meet this criterion) so the boundary had been truncated to $p<.001$. Along with a criterion of $p<.0451$ at the final analysis, this algorithm ensures an overall type I error of $\alpha=.05$. The stopping rule has a minimal effect on statistical power, less than one percentage point.

In addition to the scheduled interim analysis, the safety monitor will review cases of positive culture results and adverse events. The safety monitor will also review any cases where a patient may require additional testing to follow up on a thyroid or

renal abnormality that develops and advise on whether a wider discussion of early stopping should take place. Such cases will also be reported to the IRB.

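### Randomisation is stratified by risk group but the tests named for the irrigant effect are not; stratifying them is a small, free gain

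*Combined protocol and SAP*

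**What the plan says.** **Design.** Section D.7 states: "We project an accrual of 150 patients, resulting in 75 per treatment group". It then sets a quota: "Patients will be recruited from “low risk” and “high risk” patient populations in a 3:1 fashion, respectively". Low risk means idiopathic; high risk means everyone else. Within each group, "randomization will be split evenly between saline and betadine in a 1:1 fashion".

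**Irrigant effect.** The power table in D.7 compares 75 with 75 patients by a two-sided .05 chi-square test ("Also shown is the power of the study under each set of assumptions"). Section G compares the arms at the interim looks on the "positive culture rate before and after irrigation, using two-sample t-tests". Neither section names risk group as a stratum or covariate, and neither states a confidence interval for the irrigant effect.

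**Colonization before irrigation.** D.7 says that "150 patients will provide good statistical precision for estimating the probability of a positive pre-irrigation culture" and tabulates exact intervals for 30, 37 and 45 positives out of 150. It also plans a comparison across "subgroups such as neuromuscular and idiopathic patients, which we anticipate to accrue in approximately a 3:7 ratio", with 69%, 90% and 98% power for relative risks of 2.0, 2.5 and 3.0. This serves Aim 4 in section A.

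**The concern.** Allocation within risk groups balances the arms on risk group. If the groups differ in culture rate, that part of the variation no longer contributes to chance differences between the arms. A test that ignores the groups still counts it in its standard error, so p-values come out slightly too large and any interval slightly too wide. At stake are the effect estimate of Aim 5, which is meant to inform a later trial, and the interim p-values in section G.

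A secondary point concerns Aim 2. The pooled pre-irrigation percentage is an average whose weights come largely from the recruitment quota. D.7 gives its precision, but not the precision of either group's own rate.

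**Working it through.** **1. The plan's own figures.** With 75 per arm and the pooled-variance normal approximation, power for .12 versus .05, .04 and .03 is 33.5%, 43.8% and 55.3% (D.7 prints 33%, 43% and 55%). Exact intervals for 30, 37 and 45 of 150 are 13.9-27.3%, 18.0-32.4% and 22.8-38.0%, also as printed. The figures reproduce as an unstratified calculation.

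**2. Inputs for the check.** From D.7: 75 per arm, a 3:1 mix (about 56 low-risk and 19 high-risk per arm), a control rate of .12 and treated rates of .05 to .03. Assumed: a high:low rate ratio of 2, 2.5 or 3, the same in both arms. D.7 uses these ratios only as detectable alternatives for pre-irrigation cultures in neuromuscular versus idiopathic patients. Applying them to post-irrigation cultures and to the two risk groups is my assumption.

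**3. Standard error of the risk difference.** For an arm with overall rate p and ratio R, the low-risk rate is p/(.75 + .25R) and the high-risk rate is R times that.

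- Unstratified variance: sum over arms of p(1-p)/75.
- Stratified variance: sum over arms of [.75 pL(1-pL) + .25 pH(1-pH)]/75.

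Example, R = 3, .12 versus .05:

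- Control group rates are .08 and .24; treated group rates are .0333 and .10.
- Unstratified: (.1056 + .0475)/75 = .002041, SE .0452.
- Stratified: (.1008 + .0467)/75 = .001966, SE .0443.
- The excess is 1.9%. The 95% half-width is 8.86 points unstratified and 8.69 stratified.

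With no irrigant effect (.12 in both arms), the excess is the square root of .1056/.1008, which is 2.4%.

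**4. Size and power.** These come from simulation with strata of 56+56 and 19+19 and 400,000 or more trials per scenario. The plain chi-square has no continuity correction. With s positives among T patients in a stratum, the binomial-variance score test uses the sum of s(T-s)/(4T); the hypergeometric (usual CMH) version uses s(T-s)/(4(T-1)).

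| High:low ratio | SE excess, .12 vs .05 | SE excess, no effect | Size: chi-square | Size: stratified, binomial | Power .12 vs .05: chi-square | Stratified, binomial | CMH, hypergeometric |
|---|---|---|---|---|---|---|---|
| 1 | 0% | 0% | 5.0% | 5.0% | 34.6% | 34.7% | 33.1% |
| 2 | 0.7% | 0.8% | 4.8% | 5.0% | 34.6% | 35.0% | 33.3% |
| 2.5 | 1.3% | 1.6% | 4.7% | 5.0% | 34.5% | 35.3% | 33.8% |
| 3 | 1.9% | 2.4% | 4.5% | 5.1% | 34.5% | 35.7% | 34.3% |

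At .12 versus .03, power goes from 59.1/59.1/59.2% to 59.8/60.2/60.7% for ratios 2, 2.5 and 3.

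**5. Why the variant matters.** With exact 1:1 allocation in each stratum, the Mantel-Haenszel risk difference and relative risk equal the crude ones, so only the variance changes. The hypergeometric form multiplies the stratum variances by 112/111 and 38/37, which at these sizes outweighs the saving.

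**6. Pre-irrigation rates.** An overall 25% at a 3:1 mix means low/high rates of 20.0/40.0% (ratio 2), 18.2/45.5% (2.5) or 16.7/50.0% (3). The pooled figure therefore lies 5 to 8 points above the low-risk rate and 15 to 25 below the high-risk rate. Illustrative exact 95% intervals that split 37/150 by group are 22/112: 12.7-28.2%, and 15/38: 24.0-56.6%. That is about ±8 and ±16 points, against about ±7 for the pool.

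**7. The two mixes.** The 3:1 quota makes all non-idiopathic patients 25% of the sample. The 3:7 ratio makes neuromuscular patients alone 30% of the two groups named. Moving from 45:105 to 38:112 changes the power of the group comparison from 69.2/90.3/97.5% to 67.6/89.8/97.5%, which is under 2 points. Holding the group rates implied by 25% at 3:7, the pooled rate at 3:1 would be 24.0, 23.7 or 23.4%.

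**The case against.** The strongest reply is that nothing goes wrong under the present plan. A test with true size 4.5 to 4.8% is valid. The pilot openly accepts low power, and section G treats its stopping boundary as a prompt for discussion. The gain of 0.4 to 1.2 points of power appears only with the binomial variance; the usual CMH test would lose 0.2 to 1.2 points for ratios 2 to 3. The ratios are borrowed from pre-irrigation cultures, the calculation assumes exact balance within strata, and D.2 describes only envelopes, with no blocking. The chi-square is named for the power table, so its use in the final analysis is an inference. All of this stands, and it keeps the point small. It does not remove the mismatch between how patients are randomised and how the arms are to be compared.

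Three stronger readings are tempting, and the documents do not support them:

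- **That D.7 expects a 2- to 3-fold difference between the groups.** It gives those ratios as differences the study could detect.
- **That the plan treats all its data as one unstratified sample.** Aim 4 and D.7 plan and power a neuromuscular versus idiopathic comparison of pre-irrigation rates.
- **That the 150-patient table overstates precision for high-risk patients.** It claims precision for the overall rate only. The gap is that no group-specific precision is given.

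**Conclusion.** The point holds as a free improvement with a small gain. It is not an error that would mislead. The tests named for the irrigant effect ignore the strata used for allocation and are slightly conservative if risk group is prognostic. For ratios of 2 to 3, carried over to post-irrigation cultures and equal in both arms, the standard error is 0.7 to 2.4% too large. On a 95% half-width of 8.86 points at .12 versus .05, that is 0.06 to 0.17 points. If the groups do not differ after irrigation, there is neither gain nor loss with the binomial-variance test. No conclusion of a pilot with a stated 33% power turns on this.

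The reporting point on colonization is secondary but useful. High-risk patients, in whom the Background reports the higher infection rates, would have an interval of roughly ±16 points, and the plan does not show it. The 3:1 and 3:7 statements must be reconciled, although the effect on power is slight.

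**What to change.** 1. In D.7 and G, state that the irrigants will be compared by a Mantel-Haenszel/Cochran score test stratified on the two randomisation risk groups, **with the binomial variance**, at the interim looks and at the end. Name the variance explicitly, because the default CMH output would forfeit the gain.
2. State that the Mantel-Haenszel risk difference and relative risk will be reported with 95% confidence intervals.
3. In D.7, add that the pre-irrigation rate will be reported with an exact 95% interval for each risk group, and label the pooled rate as specific to the recruited mix.
4. Reconcile the 3:1 quota with the 3:7 mix, and say how the neuromuscular subgroup relates to the high-risk stratum.

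The cost is a few sentences. No patients or new data are needed, because risk group must already be known in order to randomise.

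### Section G's stopping rule tests the culture rate before and after irrigation, while D.7's power and the stated .05 error rate fit only a single comparison of the post-irrigation rate

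*Combined protocol and SAP*

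**What the plan says.** D.4 lists the proportion positive before irrigation and the proportion positive after irrigation as separate endpoints. It calls neither primary and lists no change endpoint.

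Every between-arm treatment figure in D.7 concerns the post-irrigation rate: .12 against .05, .04 or .03, the relative risks, the table of observed reductions, and power of 33%, 43% and 55%. The test appears only as an assumption behind the power row: "Also shown is the power of the study under each set of assumptions, assuming a two-sided $\alpha=.05$ chi-square test". D.7 also says "Positive cultures before and after irrigation will be monitored to establish the efficacy of povidone-iodine irrigation", and D.3.b says the second sample is taken "from the same location to determine reduction in the incidence of bacterial contamination achieved by" each irrigant.

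Section G sets the stopping comparison as the "primary endpoint, positive culture rate before and after irrigation, using two-sample t-tests". The boundaries are p<.001 and p<.0141. The last is introduced with "Along with a criterion of $p<.0451$ at the final analysis", and no test is named there. The three together are said to hold overall type I error at .05.

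**The concern.** D.7 and section G do not describe the same comparison. D.7's power belongs to one test of one binary outcome. Section G's rule names two cultures and uses the plural for its tests. That can mean a t-test on each patient's change, or one t-test before irrigation and another after. The first does not have D.7's power. The second does not have section G's error rate, and half of it compares the arms on a culture taken before either irrigant is used.

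The pilot is justified on the ground that "the study should provide useful preliminary information about the size of the treatment effect", from about 13 expected post-irrigation positives (75 × .12 + 75 × .05 = 12.75). With so few events, the choice of comparison can change what the pilot appears to show, so it should be fixed before anyone sees unblinded data.

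**Working it through.** **Inputs.** From D.7: 75 per arm; post-irrigation rates p = .12 (control) and .05 (povidone-iodine); pre-irrigation rate π = .25 in both arms; two-sided .05. From section G: boundaries .001, .0141 and .0451, with looks at 25, 50 and 75 per arm. Assumed, because the documents do not give it: the before/after link, P(post+|pre+) ÷ P(post+|pre−), from 1 (none) to its maximum (control values .48 and 0), with the relative risk constant.

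**1. The plan's own figure.** Mean rate .085.
- SE under no difference: √(2 × .085 × .915/75) = .0455
- SE under the alternative: √((.12 × .88 + .05 × .95)/75) = √(.1531/75) = .0452
- Power: Φ((.07 − 1.96 × .0455)/.0452) = 33.5%

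The other two columns give 43.8% and 55.4%. The printed 33%, 43% and 55% reproduce. By exact enumeration the first is 34.6%, the same for the chi-square test and the two-sample t-test.

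**2. Section G as a change score.** Randomisation makes the expected difference in change the same 7 points, but the pre-irrigation culture adds noise. With a = P(post+|pre+), per-patient variance in an arm is p(1−p) + π(1−π) − 2π(a − p).

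| Link | Variance, control | Variance, povidone-iodine | SE of difference | Variance ÷ .1531 | Power |
|---|---|---|---|---|---|
| none (a = .12; .05) | .2931 | .2350 | .0839 | 3.4 | 13% |
| 5-fold (a = .30; .125) | .2031 | .1975 | .0731 | 2.6 | 16% |
| maximum (a = .48; .20) | .1131 | .1600 | .0603 | 1.8 | 21% |

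The fourth column is √(sum of the two variances/75). Power is Φ(.07/SE − 1.96) plus a negligible opposite tail. Simulation (200,000 trials per link, with risk groups) gives 12.6% to 21.1% for a single look at .05, and 12.2% to 20.6% over the three looks. The post-irrigation rate alone has about 33% over three looks.

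**3. Section G as separate tests before and after.** Each culture alone, tested at .001/.0141/.0451, has a size of about .05. Two independent cultures would give 1 − .95² = 9.75%. In simulation with no treatment effect, the chance that at least one culture crosses at any look is about 10% with no link, falling to about 9% at the maximum link. The post-irrigation rate alone gives 5.1-5.3%. At the two interim looks only, the nominal levels bound the chance at .001 + .0141 = .0151 for one culture and .0302 for two.

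**4. Using the pre-irrigation culture as a stratum.** Mantel-Haenszel risk difference for the post-irrigation rate, against the unadjusted comparison in the same simulated trials:

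| Link | 1 | 1.8 | 3 | 5 | 9 | 21 | max |
|---|---|---|---|---|---|---|---|
| Variance, % | +1 | 0 | −3 | −7 | −12 | −19 | −28 |
| Power, points | −1.5 | −1.4 | −0.6 | +0.7 | +2.6 | +5.4 | +9.0 |

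Power breaks even at about 3.9-fold.

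**The case against.** The strongest reply is that the intended analysis is clear enough. D.4 has the after-irrigation proportion as its own endpoint, D.7 builds every treatment figure on it and mentions one test, and no passage mentions a change score. On that outcome the chi-square and t-tests have identical power, so the t-test label alone does no harm. The stopping rule is also only a prompt for discussion, and D.7 openly states that power is low.

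Most of this stands. An unnamed final test would by itself be missing detail, and the guideline status of the rule softens the consequences. What does not go away is that section G states a rule and names both cultures in it, and neither way of carrying that out matches the plan's own power or error rate.

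A reader might infer more than the documents support:

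- **That the permitted analyses span a still wider range of power.** Fisher's exact test (23.8%) and clearance among initially positive patients (about 45-52%) can be computed, but no passage proposes either.
- **That the plan errs by not adjusting for the pre-irrigation culture.** The unadjusted test is valid. Adjustment gains power only above about a 4-fold link, and the documents do not give the link.
- **That D.7's 33% is wrong.** It reproduces.

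D.2 does not say when the envelope is opened relative to the first sample. That is a separate question and no part of this point.

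**Conclusion.** The point holds as a mismatch between section G and D.7. Section G's endpoint, taken as written, gives either about 13-21% power at .12 vs .05 instead of 33%, or about a 9-10% chance of crossing a boundary under no effect instead of .05. The 13-21% rests on a pre-irrigation rate of 25% and covers the whole range of links. At pre-irrigation rates of 20% and 30%, with links of 1- to 9-fold, it is 14.0-19.0% and 12.3-15.5%. The 9-10% counts all three looks; the two interim looks contribute at most about 3%.

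This is a matter of specification. It does not show that the trial lacks a valid analysis, since the post-irrigation comparison is available and sound. It is worth correcting because the correction is small and must be made before the first unblinded look.

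**What to change.** In section G and D.7, state that the single treatment comparison at both interim looks and at the final analysis (.001/.0141/.0451) is the post-irrigation positive culture rate, not the change and not the pre-irrigation rate. Name the chi-square test that D.7's power assumes, in place of the t-tests, and report the risk difference with its 95% CI. Pre-irrigation rates would then be described by arm and not tested against the boundaries.

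Add a pre-specified Mantel-Haenszel risk difference for the post-irrigation rate, stratified by pre-irrigation culture (positive or negative). Whether this or the unadjusted comparison is the main analysis is the investigators' choice, to be fixed before any unblinded look.

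The cost is a few sentences and no new data. If the stratified analysis is made the main one, it costs at most about 1.5 points of power when the link is weak and gains up to about 9 points when it is strong. At the first look it would be sparse: about 4 events in 50 patients (25 × .17 = 4.25), with the statistic undefined in about 1% of trials. There p<.001 is reached in at most 0.2% of trials under any of the tests, so the choice hardly matters at that look.
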